### **8.4. Demographics**

Review the subject's demographics against the eligibility criteria.

### **8.5. Pharmacokinetic/Pharmacodynamic Assessments**

#### **8.5.1. Pharmacokinetic (PK) Assessment(s)**

Pharmacokinetic blood samples will be collected, processed, and shipped as detailed in the SoEs and in the Laboratory Processing Specifications as detailed in Section [10.5](#).

Allowable time windows for PK blood samples are provided in Section [10.7](#).

Quizartinib and AC886 showed temperature- and concentration-dependent partitioning into blood cells; therefore, blood samples must be processed at room temperature for determination of plasma quizartinib and AC886 concentrations.

#### **8.5.2. Pharmacodynamic Assessment(s)**

No pharmacodynamic assessments are planned for this study.

## 8.6. Safety Assessments

### 8.6.1. Reporting of Exposure to COVID-19 (SARS-CoV-2)

All confirmed or suspected COVID-19 events must be recorded in the eCRF.

- Subjects who test positive for COVID-19 should be reported as “Confirmed COVID-19”, either as an AE or SAE.
- Subjects whose medical history and clinical manifestations, signs, and possible exposure are consistent with COVID-19 but for whom no polymerase chain reaction (PCR) or antibody test for COVID-19 is available should be reported as “Suspected COVID-19”, either as an AE or SAE.

The usual protocol mandated SAE reporting requirements should be followed for confirmed or suspected COVID-19 (or SARS-CoV-2) as done for any other AE, i.e., the Investigator should assess whether any seriousness criteria are met per protocol, and appropriate protocol reporting requirements should be followed.

In the event that the Investigator assesses that a COVID-19 case does not meet any seriousness criteria as outlined in the protocol, it should be reported as a non-serious AE in the case report form (CRF).

When assessing the severity of the COVID-19 AE, the severity grading criteria as defined in Section 10.4.3 will be used.

All study drug interruption or dose reduction or discontinuation due to the COVID-19 event must be recorded on the AE and drug administration eCRFs.

For both serious and non-serious COVID-related AEs, the following information should be provided as a minimum:

- Date and laboratory results confirming the COVID-19 diagnosis (including viral antigen test and/or antiviral antibody serological test) in the laboratory eCRF, if available.
- Clinical course of the case, including presenting signs, symptoms, exposure, actions taken with the investigational products, medications used for treatment or prophylaxis of COVID-19, and outcome in relevant eCRF (e.g., concomitant medication, AE).
- Findings from diagnostic imaging (including computed tomography [CT] scan or other chest imaging).

## 8.6.2. Adverse Events

### 8.6.2.1. Method to Detect Adverse Events

The definitions of an AE or SAE can be found in Section 10.4. Adverse events may be directly observed, reported spontaneously by the subject or by questioning the subject (or, when appropriate, by a caregiver, surrogate, or the subject's legally authorized representative) at each study visit. Subjects should be questioned in a general way, without asking about the occurrence of any specific symptoms. The Investigator must assess all AEs to determine seriousness, severity, and causality. The Investigator and any qualified designees are responsible for

detecting, documenting, and recording events that meet the definition of an AE or SAE and remain responsible for following AEs that are serious, considered related to the study drug or study procedures, or that caused the subject to discontinue.

All clinical laboratory results, vital signs, and ECG results or findings should be appraised by the Investigator to determine their clinical significance. Isolated abnormal laboratory results, vital sign findings, or ECG findings (i.e., not part of a reported diagnosis) should be reported as AEs if they are symptomatic, lead to study drug discontinuation, lead to dose reduction, require corrective treatment, or constitute an AE in the Investigator's clinical judgment.

Medical conditions (including laboratory values/vital signs that are out of range) that were diagnosed or known to exist prior to informed consent will be recorded as part of medical history.

#### **8.6.2.2. Time Period for Collecting Adverse Events, including AESIs and Serious Adverse Events**

For all randomized subjects, all AEs occurring after the subject signs the ICF and that are followed to resolution up to 30 days after the EOS, whether observed by the Investigator or reported by the subject, will be recorded as detailed in Section 10.1.6.2. All SAEs will be followed until resolution, stabilization, the event is otherwise explained, or the subject is lost to follow-up.

#### **8.6.2.3. Reporting Procedure for Investigators**

All AEs (including AESIs and SAEs) will be reported and recorded. All AEs (serious and non-serious) must be reported with the Investigator's assessment of seriousness, severity, and causality to the study drugs.

Always report the diagnosis as the AE or SAE term. When a diagnosis is unavailable, report the primary sign or symptom as the AE or SAE term with additional details included in the narrative until the diagnosis becomes available. If the signs and symptoms are distinct and do not suggest a common diagnosis, report them as individual entries of AE or SAE.

#### **8.6.2.4. Serious Adverse Events Reporting**

The following types of events should be reported by the Investigator within 24 hours of awareness:

- SAEs (Section 10.4.2)
- Hepatic events (both serious and non-serious) meeting the laboratory criteria of a potential Hy's Law criteria (as defined in Section 8.6.2.7).
- QTcF prolongation, TdP, and other ventricular arrhythmias (as defined in Section 8.6.2.7)

Details summarizing the course of the SAE, including its evaluation, treatment, and outcome should be provided. Specific or estimated dates of AE onset, treatment, and resolution should be included. Medical history, concomitant medications, and laboratory data that are relevant to the event should also be summarized in the SAE report. For fatal events, the SAE report should state whether an autopsy was or will be performed and should include the results if available. Source

documents (including medical reports) will be retained at the study site and should not be submitted to the Sponsor for SAE reporting purposes.

Call the local SAE Hotline or your study monitor for any questions on SAE reporting.

See Section [8.6.2.2](#) for details on the time period for collecting SAEs.

#### **8.6.2.5. Reporting Requirement to Sites and Regulatory Authorities**

The CRO will inform the Sponsor of any suspected unexpected serious adverse reactions (SUSARs) occurring in study sites or other studies of efavirenz and quizartinib, as appropriate per institutional and/or local reporting requirements.

The Sponsor will comply with any additional local safety reporting requirements. The Sponsor will assess if an AE is to be considered “unexpected” based on the “Reference Safety Information” section in the current IB.

#### **8.6.2.6. Follow-up for AEs and SAEs**

The Investigator is obligated to perform or arrange for the conduct of supplemental measurements and/or evaluations as medically indicated to elucidate the nature and/or causality of the AE or SAE as fully as possible. This may include additional laboratory tests or investigations or consultation with other health care professionals.

Urgent safety queries must be followed up and addressed promptly. The Investigator will submit any updated SAE data to the Sponsor within 24 hours of receipt of the information. Follow-up information and response to non-urgent safety queries should be combined for reporting to provide the most complete data possible within each follow-up report.

#### **8.6.2.7. Adverse Events of Special Interest**

##### **8.6.2.7.1. Hepatic Events**

Hepatic events (both serious and non-serious) which meet the potential Hy’s Law criteria defined as an elevated (ALT and/or AST)  $\geq 3 \times$  ULN and an elevated total bilirubin  $> 2 \times$  ULN, that may occur at different time points during the study conduct, should always be reported to the Sponsor. These events must be reported with the Investigator’s assessment of seriousness, severity, causality, and a detailed narrative. These events should be reported within 24 hours of Investigator’s awareness of the event regardless of seriousness. A targeted questionnaire will be available as an eCRF to collect relevant additional information for these potential cases.

If the subject discontinues study drug due to liver enzyme abnormalities, the subject will have additional clinical and laboratory evaluations as described in Section [10.2](#) in order to determine the nature and severity of the potential liver injury.

##### **8.6.2.7.2. QTcF Prolongation, Torsades de Pointe, and Other Ventricular Arrhythmias**

Subjects who experience  $> 480$  msec QTcF prolongation must be monitored closely with ECGs, performed twice weekly for the first week of the QTcF prolongation and then weekly thereafter until the QTcF prolongation is resolved. QTcF prolongation  $\geq$  Grade 3, either serious or non-serious and whether or not causally related, must be recorded as an AE or SAE in the eCRF

within 24 hours of the assessment, with the Investigator's assessment of seriousness, causality, and a detailed narrative.

Monitoring in subjects with QTcF prolongation will include the following:

- Electrolytes (potassium, calcium, and magnesium) should be checked and supplementation given to correct any values outside the normal range.
- Concomitant medications should be reviewed to identify and, if appropriate, discontinue any medication with known QT prolonging effects.

#### **8.6.2.8. Overdose**

An overdose is defined as the accidental or intentional administration of any dose of a product that is considered both excessive and medically important. All occurrences of overdose must be reported to the Sponsor within 24 hours of awareness and recorded via the SAVER/Overdose Form and eCRF.

An "excessive and medically important" overdose includes any overdose in which either an SAE, a non-serious AE, or no AE occurs and is considered by the Investigator as clinically relevant, i.e., poses an actual or potential risk to the subject. Occupational exposures must be reported via the SAVER form.

#### **8.6.2.9. Pregnancy**

It is the responsibility of the Investigator or designee to notify the Sponsor of any pregnancy in a female subject or in a male subject's female partner that occurs while the subject is receiving or within 6 months of having received the dose of quizartinib. Although pregnancy is not technically an AE, all pregnancies must be followed to conclusion to determine their outcome. If a pregnancy is reported, the Investigator should inform the Sponsor within 24 hours of learning of the pregnancy as this information is important for drug safety and public health concerns.

The Investigator should make every effort to follow the female subject or partner of a male subject (upon obtaining written consent from partner) until completion of the pregnancy and record the complete pregnancy outcome information, including normal delivery or induced abortion. Any adverse pregnancy outcome, either serious or non-serious, should be reported in accordance with study procedures. If the outcome of the pregnancy meets the criteria for immediate classification as an SAE (i.e., post-partum complications, spontaneous or induced abortion, stillbirth, neonatal death, or congenital anomaly, including that in an aborted fetus), the Investigator should follow the procedures for reporting SAEs.

For reports of pregnancy in a female subject or a female partner of a male subject, the EIU Reporting Form (or SAE form if associated with an adverse outcome) should be completed with the subject's randomization number, initials, and date of birth, and details regarding the female partner should be entered in the narrative section.

#### **8.6.2.10. Pregnancy Testing**

Women of childbearing potential will have a serum pregnancy test conducted at Screening and at Check-in and the results documented. For eligibility (as defined in Section 5.1), a serum pregnancy test must be performed with the results available prior to enrollment.

Women who are postmenopausal will have a follicle-stimulating hormone (FSH) test conducted at Screening.

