### 1.3. Schedule of Events

**Table 1.1: Treatment Group A**

Study Period	Screening a	Check-in	Treatment Period								EOS/ET b
Study Day	Day -21 to Day -1	Day -1	Days 1 - 14	Day 15		Day 16	Day 17	Day 18	Day 19	Days 20 - 35	Day 36
PK Samples Postdose (hours)				Predose	<24	24	48	72	96	144 - 432	504
Procedures											
Informed Consent	X										
Inclusion/Exclusion Criteria	X	X									
Demographic Information	X										
Medical/Surgical History	X	X									
Prior/Concomitant Medications	<-----continuous----->										
Complete Physical Examinations c	X	X	X								X
Body Weight and BMI d	X	X									X
Height	X										
Urine Drugs of Abuse and Alcohol Screen	X	X									
Virology (HBsAg/HIV/HAV/HCV)	X										
Serum Pregnancy Test (WOCBP) e	X	X									
FSH f	X										
Hematology, Serum Chemistry g	X	X	X	X					X	X	X
Coagulation (PT, INR)	X	X		X					X		X
Urinalysis	X	X							X		X
12-lead ECGs h	X	X		X	X						X
Vital Signs (BP, pulse, respiratory rate, oral temperature) i	X	X		X	X						X
Efavirenz Administration j			X	X	X	X	X	X	X	X	
Quizartinib Administration k				X							
PK Blood Samples l				X	X	X	X	X	X	X	X
PGx Sample				X							

Study Period	Screening a	Check-in	Treatment Period									EOS/ET b
Study Day	Day -21 to Day -1	Day -1	Days 1 - 14	Day 15		Day 16	Day 17	Day 18	Day 19	Days 20 - 35	Day 36	
PK Samples Postdose (hours)				Predose	<24	24	48	72	96	144 - 432	504	
Procedures												
AE Monitoring	X	X		<-----	continuous	----->						
Check-in		X										
Confinement			<-----	continuous	----->							
Discharge												X

AE = adverse event; BMI = body mass index; ECG = electrocardiogram; EOS = end-of-study; ET = early termination; FSH = follicle-stimulating hormone; HAV = hepatitis A virus; HBsAg = hepatitis B virus surface antigen; HCV = hepatitis C virus; HIV = human immunodeficiency virus; INR = international normalized ratio; PGx = pharmacogenomic; PK = pharmacokinetic; PT = prothrombin time; WOCBP = women of childbearing potential

- a To be conducted within 21 days prior to dosing
- b Following final blood collections; same procedures to be performed at ET as at EOS.

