- c A full physical examination that includes an evaluation of the head, eyes, ears, nose, and throat and the cardiovascular, dermatological, musculoskeletal, respiratory, gastrointestinal, and neurological systems will be performed at Screening, and on Day -1, Day 14, and EOS.
- d BMI at Screening only
- e Female subjects (WOCBP only)
- f Naturally postmenopausal female subjects only
- g Blood samples for hematology and serum chemistry will be collected after a 10-hour fast at Screening, and on Day -1, Day 7, predose (quizartinib) on Day 15, and on Day 19, Day 27, and EOS.
- h Triuplicate ECG (approximately 2 minutes apart) and after at least 5 minutes of quiet rest in the supine position. When a blood collection is scheduled concomitantly with an ECG, the ECG should be taken at least 5 minutes prior to the blood collection and at predose, 2, 4, and 8 hours after quizartinib administration.
- i Vital signs will be taken after at least a 5-minute supine rest; vital signs should be taken at all ECG timepoints.
- j Efavirenz will be dosed as 600 mg once daily from Day 1 through Day 35. Efavirenz will be taken before bedtime on an empty stomach (no food for at least 2 hours before and after dosing).
- k A single dose of 60-mg quizartinib (2 × 30 mg) will be administered following an overnight fast of 10 h on Day 15. Water consumption will be restricted from 1 hour predose to 2 hours postdose, except for the 240 mL of water that is to be administered with quizartinib. Subjects will continue to fast for 4 hours postdose.
- l Day 15 through 36 (relative to quizartinib) PK samples for quizartinib will be collected at predose, 1, 2, 4, 6, 8, 12, 24, 48, 72, 96, 144, 216, 288, 360, 432, and 504 hours post-quizartinib dose. Quizartinib and AC886 showed temperature- and concentration-dependent partitioning into blood cells; therefore, blood samples must be processed at room temperature for determination of plasma quizartinib and AC886 concentrations.

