### 5.1. Inclusion Criteria

Subjects eligible for inclusion in this study have to meet all inclusion criteria for this study.

1. Voluntarily consents to participate in this study and provides written informed consent before the start of any study-specific procedures.
2. Male and female subjects 18 to 55 years of age (inclusive), with a body mass index (BMI) of 18 kg/m^2 to 32 kg/m^2 (inclusive) at Screening.
3. In females, documented surgical sterilization, postmenopausal status for at least 1 year (follicle stimulating hormone [FSH] > 40 mIU/mL serum at Screening), or agreement to have sterile male partner, or agreement to use 1 of the protocol-approved means of contraception from Screening until 6 months after the dose of quizartinib. See Section 5.3 Contraception Requirements.
4. In males, documented surgical sterilization, or sexual abstinence, or agreement to use 1 of the protocol-approved means of contraception from Screening until 6 months after the dose of quizartinib. See Section 5.3 Contraception Requirements.
5. In females, must not retrieve eggs/ova via assisted reproductive technology (ART) either for their own use or donation while on study or for 6 months after the last dose of quizartinib, whichever is later.
6. In males, agreement to avoid sperm donation for 6 months after the dose of quizartinib.
7. Has vital signs (measured after subject has been supine for at least 5 minutes) at Screening within the following ranges: heart rate: 50–100 bpm; systolic blood pressure (BP): 90–145 mmHg; diastolic BP: 50–95 mmHg. Out-of-range vital signs may be repeated once.
8. Has liver function test results (ALT, AST, and total bilirubin) equal to or below the upper limit of normal. Hemoglobin levels must be at least 11.5 g/dL for female subjects and at least 12.5 g/dL for male subjects.
9. Must agree to refrain from donation of blood from 56 days prior to Screening, plasma from 2 weeks prior to Screening, and platelets from 6 weeks prior to Screening.
10. Must be willing to refrain from consuming blood oranges, grapefruit, grapefruit juice, pomegranates, pomegranate juice, Seville (bitter) oranges, and star fruit from 10 days before Day -1 until EOS.
11. Is willing and able to remain in the study unit for the entire duration of the confinement period.

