### **Laboratory Tests**

19. Is a female with a positive pregnancy test result or is lactating.
20. Laboratory results (serum chemistry, hematology, and urinalysis) outside the normal range, if considered clinically significant by the Investigator. Estimated glomerular filtration rate (eGFR) <90 mL/min (calculated using the Cockcroft-Gault Equation equation) at Screening.
21. Has a positive serology for hepatitis B surface antigen (HBsAg), hepatitis C virus (HCV), hepatitis A virus (HAV) immunoglobulin M (IgM), or human immunodeficiency virus (HIV).
22. Has a positive urine screen for drugs of abuse or for ethanol at Screening or at Check-in on Day -1.
23. Current enrollment in or have not yet completed receiving an investigational device or product (at least 30 days or 5 elimination half-lives, whichever is longer) within 30 days of the dose of quizartinib.

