## 5.3. Contraception Requirements

### Female Subjects

Females of childbearing potential must use contraception while enrolled in this study.

From Screening until 6 months after the dose of quizartinib:

- Sterile male partner
- Any of the following with spermicide:
  - Non-hormonal IUD
  - Female or male condom
  - Contraceptive sponge
  - Diaphragm
  - Cervical cap

Any of the following hormonal contraceptives may be started only after Day 36 for Treatment Group A and Day 22 for Treatment Group B. However, one of the non-hormonal methods listed above must be used in conjunction with the hormonal contraceptive for 2 weeks until the hormonal contraceptive becomes effective, and then the hormonal contraceptive must be continued until 6 months after the dose of quizartinib:

- Hormonal IUD
- Intravaginal system
- Oral, implantable, transdermal, or injectable contraceptive

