## **6.7. Prohibited Therapies/Products**

The following (except medications approved by the Sponsor on a case-by-case basis) are prohibited within 14 days (or 5 drug half-lives, if 5 drug half-lives were expected to exceed 14 days) before Day -1 and throughout the study:

- Hormonal contraceptives and all other prescription medications, including CYP3A inhibitors and inducers (see Section [10.3.2](#)) or unless included in Section [6.8](#)
- Hormonal replacement therapy (can be started at any time **after EOS**)
- Medical marijuana
- Melatonin and all other OTC products
- Echinacea, gingko biloba, ginseng, kava kava, St. John's wort, and all other herbal products
- Vitamins and minerals generally consistent with daily requirements are permitted during the 14 days before Day -1. However, all dietary supplements are prohibited starting on Day -1 and throughout the study.
- Blood oranges, grapefruit, grapefruit juice, pomegranates, pomegranate juice, Seville (bitter) oranges, and star fruit are prohibited for 10 days before Day -1 and throughout the study.
- Alcohol, xanthine-containing beverages, or foods including regular coffee, regular tea, caffeine-containing soft drinks and energy drinks, and chocolate are prohibited for 72 hours before Day -1 and throughout the study.

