## 7. WITHDRAWAL/DISCONTINUATION FROM THE STUDY

### 7.1. Subject Withdrawal/Discontinuation from the Study

Subjects may discontinue from the study for any of the following reasons:

- Adverse event
- Withdrawal by subject
- Investigator decision
- Pregnancy
- Protocol deviation
- Study termination by Sponsor
- Other

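### Group A's last serum pregnancy test is 15 days before quizartinib; a Day 14 retest is a cheap, low-severity safeguard, not the correction of an error

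*Combined protocol and SAP*

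**What the plan says.** Section 8.6.2.10 (Pregnancy Testing) states: "Women of childbearing potential will have a serum pregnancy test conducted at Screening and at Check-in and the results documented". The result used for eligibility must be available before enrollment. Table 1.1 agrees: the row beginning "Serum Pregnancy Test (WOCBP" is marked at Screening and Day -1 only, with nothing in the Treatment Period or at end of study.

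Group A takes efavirenz at bedtime on Days 1 to 35 and a single quizartinib dose on the morning of Day 15. Group B takes quizartinib on Day 1.

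Other provisions that bear on the point:

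- **Exclusion and discontinuation.** Exclusion criterion 19 reads: "Is a female with a positive pregnancy test result or is lactating". Section 7.1 lists pregnancy under "Subjects may discontinue from the study for any of the following reasons".
- **Contraception (5.3).** Women of childbearing potential must use contraception from Screening until 6 months after quizartinib. The choices are a sterile partner, or an item from the list headed "Any of the following with spermicide" (a non-hormonal IUD or a barrier method). Section 6.7 prohibits hormonal methods during the study, "except medications approved by the Sponsor on a case-by-case basis".
- **Confinement.** Inclusion criterion 11 reads: "Is willing and able to remain in the study unit for the entire duration of the confinement period". Table 1.1 shows confinement as continuous.
- **Blood already drawn.** Footnote g of Table 1.1 schedules Group A hematology and chemistry at Screening, Day -1, "Day 7, predose (quizartinib) on Day 15, and on Day 19, Day 27, and EOS". Coagulation, ECG and vital signs are also repeated predose on Day 15, and a physical examination is done on Day 14.

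**The concern.** Several safety checks are refreshed in Group A just before quizartinib, but the pregnancy test is not. The residual case is a conception in the days before check-in that is still undetectable on Day -1. Confinement cannot address it because it starts at check-in. Contraception lowers its chance without removing it.

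Such a subject could go on to receive quizartinib and the remaining efavirenz. Section 2.3 says that no benefit from either drug is intended or expected for these healthy subjects, so an avoidable exposure in early pregnancy has nothing to set against it. Group B is dosed the morning after check-in and has no comparable interval in which to retest. Group A has one, and the plan does not use it.

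**Working it through.** The plan gives no figure for this risk, so the check is a count of days and doses, followed by the effect on precision if a profile is lost.

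**Intervals** (Table 1.1; there is no Day 0). From Day -1 it is 7 days to Day 7, 14 days to Day 14 and 15 days to Day 15. In Group B, Day -1 to Day 1 is 1 day.

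**Efavirenz doses.** Bedtime doses on Days 1 to 14 give 14 before the Day 15 morning dose, leaving 35 - 14 = 21. If the Day 14 result arrives before that night's dose, 13 have been given and 35 - 13 = 22 remain.

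**What each test day could still miss.** The documents give no detection lag. Assume that serum hCG becomes detectable L days after conception, with L from 7 to 14; values of 16 and 18 are added as a stress test. A Day -1 test misses conceptions in the L days before check-in. A test d days after Day -1 still misses max(0, L - d) days of that window.

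| L (days) | Missed on Day -1 | Still missed, Day 7 (d = 7) | Still missed, Day 14 (d = 14) | Still missed, Day 15 (d = 15) |
|---|---|---|---|---|
| 7 | 7 | 0 | 0 | 0 |
| 10 | 10 | 3 | 0 | 0 |
| 14 | 14 | 7 | 0 | 0 |
| 16 | 16 | 9 | 2 | 1 |
| 18 | 18 | 11 | 4 | 3 |

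Across the assumed range, a Day 14 test closes the window and the existing Day 7 draw does not. These are lengths of a window in days, not probabilities, and they make no allowance for contraception.

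**Number affected.** Only women of childbearing potential among the 16 Group A subjects. Their number is not given and could be zero.

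**Precision if one profile is lost.** Section 9.2 assumes a CV of 35% and targets 15 per treatment for 90% confidence of being within 20% of the true ratio. With sigma = sqrt(ln(1 + 0.35²)) = 0.3399 and SE = sigma × sqrt(2/n), the probability that the estimated ratio lies between 0.80 and 1.20 times the true ratio is 89.3% at 15 per group and 90.4% at 16. The plan's figure is therefore reproduced closely.

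The 90% CI half-width on the log scale is t(0.95, df) × sigma × sqrt(1/nA + 1/nB):

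- 16 and 16: 0.2040, so the limits are the ratio divided and multiplied by exp(0.2040) = 1.226.
- 15 and 16: 0.2076, factor exp(0.2076) = 1.231.

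Losing one profile leaves 16 - 1 = 15 in Group A, exactly the per-treatment target, if there is no other dropout.

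**The case against.** The strongest reply is that the plan already handles this risk adequately. It has two serum tests, with a result required before enrollment, mandatory contraception and continuous confinement. Screening can be as early as Day -21. When it falls at least 14 days before Day -1, the whole assumed detection window lies under required contraception. The probability cannot be sized, the detection lag is an outside assumption, and the benefit is partial. All of this stands, and it keeps the severity low. It does not remove the window, and it does not explain leaving the Group A interval unused when the check costs so little.

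A reader might infer three stronger points that the documents do not support:

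- **That 15 days against 1 day is a difference in risk between the groups.** Confinement makes conception after Day -1 unlikely, so the relevant window lies before check-in and is the same in both groups. Only the opportunity to retest differs.
- **That an affected woman is certain to be dosed.** AE monitoring is continuous, a physical examination is done on Day 14, and both Investigator decision and pregnancy are discontinuation reasons. An unscheduled test is not barred, though none is required.
- **That Section 8.6.2.9 fails to cover a pregnancy found on Day 14.** Its notification sentence is tied to the quizartinib dose, but the section also requires all pregnancies to be followed to conclusion. A cross-reference would clarify this; it would not fill a large gap.

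**Conclusion.** The point holds as a cheap, low-severity improvement to subject safety. In Group A the last serum pregnancy test is 15 days before quizartinib, so a conception too early to detect at check-in could go unnoticed, and the subject could receive quizartinib and 21 further efavirenz doses. The documents show this to be unlikely but do not allow its probability to be calculated.

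It should not be read as an error or an inconsistency: Section 8.6.2.10 and Table 1.1 agree, and the eligibility testing rule is met. It has no bearing on the validity of the PK comparison.

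The preference for Day 14 over the existing Day 7 draw rests on the assumed detection lag of 7 to 14 days. With a longer lag, Day 14 would still miss part of the window. A retest prevents only later exposure: 13 or 14 efavirenz doses will already have been taken, and Group B gains nothing.

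**What to change.** In Table 1.1, mark the pregnancy test row under Days 1 - 14 and extend footnote e to specify Day 14 for Group A women of childbearing potential. The Day 15 predose draw can be used instead if the result will be back before dosing.

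In Section 8.6.2.10, add text such as: *In Treatment Group A, repeat the serum pregnancy test on Day 14 in women of childbearing potential. Quizartinib is given only after a negative result is available. If the result is positive, withhold quizartinib and efavirenz pending a confirmatory test. If it is confirmed, discontinue the subject under Section 7.1, and report and follow the pregnancy as in Section 8.6.2.9.* The confirmatory step avoids stopping both drugs permanently on one unconfirmed result.

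**Cost.** One assay per Group A woman of childbearing potential, plus one draw if done on Day 14. The Day 15 option needs no extra draw but depends on a turnaround time that the documents do not give. A confirmed pregnancy loses one Group A profile (16 to 15) and moves the 90% CI factor from 1.226 to 1.231 at a CV of 35%. That leaves no margin above the per-treatment target, and replacement needs Sponsor approval (5.4). An unconfirmed positive could also interrupt efavirenz or delay quizartinib, so the added text should say how a subject with a negative confirmatory test proceeds. Drawing early on Day 14 leaves the most time for this. The statistical analysis is unchanged.
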